**Evaluation of an Incentive-based Intervention to
Improve 90-day Adherence in PAP-Naïve Patients:
Project Dahlia**

Investigational Plan

Version: **2.0**

Date: **08Jul2019**

Protocol Number: **SLP-18-08-01**

Sponsor: **ResMed Corp**
[name]
[name]
[contact]

NCT Number: **NCT03851094**

This protocol has been written in accordance with current applicable guidelines (IDE for USA) as well as all other relevant additional references, medical and legal.

The information herein is confidential and the property of ResMed Corp. It is to be used in confidence for the conduct of the clinical trial according to written agreement.

Version History

Version	Date	Notes
1.0	10Jan2019	Original Version
2.0	08Jul2019	Removed inclusion criteria for patients to have used their device less than an average of 3.5 hours of usage in the first 3 days of therapy.

Protocol Summary

Study Design:	
This is a prospective, randomized, open-label study to evaluate effectiveness of applying financial and social incentives via a smartphone-based app in helping participants achieve adherence to therapy. Randomization will consist of an allocation ratio of 2:1 (control:treatment)
 
This study will be conducted on patients with obstructive sleep apnea (OSA) who have been prescribed ResMed flow generator for positive airway pressure (PAP).
 
Participants will be randomized to one of two groups: control or intervention with Wellth app, "Restful". The study comprises up to 2 participant contacts by phone, and 3 data collection timepoints. The first contact involves consenting and enrolling the participant, providing instructions based on the arm they are randomized to, and collecting baseline data including questionnaires. Those randomized to the intervention group will have a second contact, which involves onboarding to Restful. A second administration of the questionnaires will occur at +90 days from baseline.

Intervention:	
Restful by Wellth. The intervention is use of the Restful app, which provides a small daily financial reward for achieving therapy usage goals and social support. The app will also send a daily reminder to participants to use their therapy. There is no clinical treatment intervention, as all patients included in this trial will be receiving PAP therapy per standard of care.

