3.6 SAMPLE SIZE

N= 300

A minimum total sample size of 270 patients, with 2:1 randomization (180 in Control group, 90 in Test group) is required to yield an 80% probability of detecting a difference of 0.8 hours in mean usage (160% of the minimally clinically significant difference) when the standard deviation is 2.5 and 2.0 in the Control and Test groups, respectively. The required sample size was calculated in the Two Sample T-Tests Assuming Unequal Variances Procedure using NCSS Power Analysis Statistical Software, Version 16 (PASS 16¹⁴) based on a one-sided, two sample t-test, using a significance level of 0.025.

Assuming a potential 10% drop-out rate due to study withdrawal or lost-to-follow-up, the final sample size will be 300 patients (270/0.9), equating to 200 in the Control group and 100 in the Test Group. The 2:1 randomization ratio was chosen because it is more cost-effective to enroll subjects in the control group.

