3.7 STUDY ENDPOINTS

Primary Endpoint: mean PAP usage at 90 days collected from participants' flow generators

Secondary Endpoints:

- Percentage of participants that meet the Medicare compliance standard (at least 4 hours per day on at least 70% of the days in a consecutive 30-day period any time in the first 90 days of therapy)
- Change in ESS and FOSQ-10 questionnaire scores
- Baseline scores of perceived disease severity, claustrophobia, coping skills, and health literacy as moderators of the intervention's effectiveness

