3.8 ANALYSIS POPULATIONS

Randomized Population: all participants enrolled and randomized to treatment groups.

Intent-to-Treat (ITT) Population: all participants randomized to control or intervention group, regardless of the actual intervention received.

Evaluable Population: all ITT subjects who complete the 90-day study period and complete the end-of-study questionnaire.

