Mean change in ESS and FOSQ questionnaire scales will be compared between control and intervention groups using a mixed-effects linear model on the ITT population and a two-sample t-test on the Evaluable population. In the mixed-effects model, the response variable will be the mean questionnaire score and the model will include randomized group, visit, and a randomized group by visit interaction as fixed effects and subject as a random effect.

Baseline perceived disease severity, claustrophobia, coping skills, and health literacy will be tested as moderators of the intervention's effectiveness. Baseline scores will be regressed on the primary outcome (usage), and then in a mixed-effects model, the response variable will be usage and the model will include baseline score, randomized group, and a randomized group by baseline score interaction as fixed effects and subject as a random effect.

An exploratory analysis will examine how engagement with the study is associated with PAP usage. Engagement will be measured as app usage (number of touches). A linear regression model with PAP usage as the dependent variable and engagement as the independent variable will be fit to all ITT subjects (engagement is zero for all control subjects). An exploratory analysis will also test whether the intervention has a direct or indirect effect on the following psychosocial factors: the pros and cons of change, self-efficacy, and social support. Finally, an exploratory analysis will test whether nomination of, and the extent of engagement with, a social support person moderates the intervention effectiveness.

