4.2 INITIAL (ENROLLMENT) CONTACT

1. Provide patient with access to informed consent document.
2. When consent has been obtained, collect device information (device ECN, device settings, mask type), demographic, and baseline data into the electronic data capture (EDC) system.
3. Randomize participant in EDC.
 - a. Participants randomized to the Control group (Group A) will complete a set of baseline questionnaires.
 - b. Participants randomized to the Treatment group (Group B) will complete a set of baseline questionnaires and provided with instructions to download Restful to their smartphone.
 - c. Monitor both groups' PAP device usage per your standard of care.

[figure not shown]
4.3 90-DAY STUDY CONTACT

1. Both Group A and Group B will be asked to complete a set of end of study questionnaires. Restful will be 'turned off' for Group B participants.
2. Continue to monitor participants' PAP device usage per your standard of care.
3. Distribute compensation for study participation.

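### Adjusting ESS and FOSQ-10 for the baseline score already collected would gain precision on these secondary endpoints for a change of analysis wording

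*Combined protocol and SAP*

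**What the plan says.** Section 3.7 names "Change in ESS and FOSQ-10 questionnaire scores" as a secondary endpoint. Section 3.9 compares mean change between arms "using a mixed-effects linear model on the ITT population and a two-sample t-test on the Evaluable population". In the mixed model the response is the score on each questionnaire. On its terms, the section states: "the model will include randomized group, visit, and a randomized group by visit interaction as fixed effects and subject as a random effect". Neither section 3.9 nor any other section adds the baseline score as a covariate for this endpoint or holds the two arms to a common baseline mean.

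There is one baseline score and one follow-up score. The Protocol Summary states: "A second administration of the questionnaires will occur at +90 days from baseline". The Evaluable Population (section 3.8) is "all ITT subjects who complete the 90-day study period and complete the end-of-study questionnaire".

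The order of events at enrollment is not fully settled. Section 4.2 lists the questionnaires by arm, as sub-steps of the randomization step: "Participants randomized to the Control group (Group A) will complete a set of baseline questionnaires", with a parallel line for Group B. Section 3.2 places the baseline questionnaire at the initial contact after consent, without stating its order relative to randomization.

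**The concern.** A baseline score that predicts the 90-day score can be used to remove outcome variance. Subtracting it, as a change score does, fixes its coefficient at 1. Regression chooses the coefficient that minimises residual variance, so under a common slope subtraction can at best equal it. The mixed model looks as though it handles baseline, but with two visits and free arm means at each visit it returns the same contrast as the t-test.

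At stake is the precision of two patient-reported comparisons for which the plan sets no power. Section 3.6 sizes the trial on usage alone ("80% probability of detecting a difference of 0.8 hours in mean usage"), so an efficient analysis is the main protection these endpoints have.

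**Working it through.** **Inputs.** From the documents: 180 control and 90 test evaluable, 200 and 100 randomized, 10% drop-out, usage SDs of 2.5 and 2.0, one-sided level 0.025 (all section 3.6); two questionnaire time points. Assumed, because the documents give nothing: rho between baseline and 90-day score, and the SDs s0 (baseline) and s1 (90 days), with r = s0/s1.

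**1. The plan's own figure.** For usage, SE² = 2.5²/180 + 2.0²/90 = 0.0347 + 0.0444 = 0.0792, so SE = 0.281 and 0.8/0.281 = 2.84. Power is Φ(2.84 − 1.96) = 81.1%, or 80.8% with the noncentral t. The minimum N is 267 by the t calculation, and 270/0.9 = 300. The stated sample size reproduces. It says nothing about ESS or FOSQ.

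**2. The two planned methods are one method when data are complete.** With free arm means at both visits, the group-by-visit term is (test 90-day mean − test baseline mean) − (control 90-day mean − control baseline mean), which is the difference in mean change. REML fits to simulated 180:90 data at rho 0.3, 0.5 and 0.7 gave estimates identical to the t-test, with SEs equal to at least four decimals (for example 0.1372 by both at rho 0.5).

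**3. Saving with equal SDs.** In units of s²(1/n₁ + 1/n₂), the variance is 2(1 − rho) for the change score and 1 − rho² for ANCOVA. The ratio is (1 + rho)/2 and the saving is (1 − rho)/2.

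| rho (assumed) | Change score | ANCOVA | Ratio | Saving | Change-score N matching ANCOVA at 270 | Power after adjustment if change score has 80% |
|---|---|---|---|---|---|---|
| 0.3 | 1.40 | 0.91 | 0.65 | 35% | 415 | 93.5% |
| 0.5 | 1.00 | 0.75 | 0.75 | 25% | 360 | 89.9% |
| 0.7 | 0.60 | 0.51 | 0.85 | 15% | 318 | 86.0% |
| 0.8 | 0.40 | 0.36 | 0.90 | 10% | 300 | 84.0% |

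The N column is 270/ratio. The power column is Φ((1.960 + 0.842)/√ratio − 1.960), borrowing the one-sided 0.025 level from section 3.6.

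**4. Saving with unequal SDs.** The general saving is (r − rho)²/(1 + r² − 2·rho·r), which is never negative.
- r = 0.8: 0.25/1.16 = 22% at rho 0.3, falling to 0.01/0.52 = 2% at rho 0.7.
- r = 1.25: 0.9025/1.8125 = 50% at rho 0.3, falling to 0.3025/0.8125 = 37% at rho 0.7.

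**5. Missing 90-day scores.** With 10% missing at random, the planned mixed model recovers a little from participants who have a baseline score only. In 6,000 simulated 200:100 trials per scenario (covariance known), a common baseline mean saved 33.7%, 22.7% and 13.7% of the planned model's variance at rho 0.3, 0.5 and 0.7, and 36.2%, 25.0% and 15.0% against the t-test. The closed form against the mixed model, 0.9(1 − rho)/[(1 + rho) + 0.9(1 − rho)], gives 32.6%, 23.1% and 13.7%, which agrees within simulation error.

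**6. Chance baseline imbalance.** With equal SDs, a baseline difference D between arms leaves an expected error of rho·D − D = −(1 − rho)D in the change-score estimate: −0.7D, −0.5D and −0.3D at rho 0.3, 0.5 and 0.7.

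**The case against.** The strongest reply is that this is a choice and not an error. Section 3.7 defines the endpoint as change, both planned methods estimate the difference in change validly under randomization, and no power target exists for them to miss. That stands. It is no reason to keep the less precise estimator, though: an ANCOVA with change as the response and baseline as a covariate gives exactly the same group effect as one with the 90-day score as the response, so the endpoint is preserved.

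The second reply is that the size of the loss rests on values absent from the documents. That also stands. A reader might infer that the plan simply wastes 15–35% of the variance. The documents do not support a flat figure: the only SDs they give are for PAP usage, and the range is what rho 0.3–0.7 with equal SDs produces.

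A reader might also infer that regression to the mean magnifies chance imbalance, as a second harm. It does not. Under equal SDs and positive rho the carry-over is smaller than D and opposite in sign, and it averages to zero over randomization if baseline is unaffected by allocation. It is the lost precision described another way.

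Finally, if baseline answers can follow knowledge of allocation, a common-baseline assumption is itself open to challenge. That is a fair precondition for the fix, but a change score computed from the same answers has the same weakness. Nor do the documents establish that answers do follow it: section 4.2 lists the questionnaires under the randomization step, while section 3.2 leaves the order open.

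**Conclusion.** This is a free improvement in precision on secondary endpoints. The planned analyses are valid, and a reader should not infer bias, nor any consequence for the primary usage analysis or for the sample size of 270 inflated to 300.

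The direction is secure: under a common slope in both arms, baseline adjustment cannot increase the large-sample variance. The size is conditional on rho and on the SD ratio, neither of which the plan gives. A central case of equal SDs and rho 0.5 saves a quarter of the variance. The plausible span runs from almost nothing (r = 0.8, rho 0.7) to about half (r = 1.25, rho 0.3). For the ITT mixed model with 10% missing, the equal-SD savings are about 34%, 23% and 14% at rho 0.3, 0.5 and 0.7, slightly below those against the t-test.

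**What to change.** **Analysis wording (section 3.9).**
- Evaluable population: replace the two-sample t-test with ANCOVA of the 90-day score on randomized group and baseline score.
- ITT population: keep both visits as responses but constrain the arms to a common baseline mean, preferably with an unstructured two-visit covariance so that unequal SDs are allowed. Alternatively, adjust for the baseline score and take only the 90-day score as the response; baseline should not be both response and covariate.

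This costs a few sentences and needs no new data or participants. It should be settled before outcome data are examined, so that the choice cannot appear driven by results.

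**Procedure (section 4.2), separately.** Place the baseline questionnaires ahead of the randomization step and state the same order in section 3.2. The common-baseline assumption is clean only if answers precede knowledge of allocation. This is a small change to the enrollment sequence, not an analysis edit, and it would be worth making even if change scores were kept.

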3.2 STUDY DESIGN

This is a prospective, randomized, two-arm, open-label study to evaluate effectiveness of applying financial and social incentives via a smartphone-based app in helping participants achieve adherence to therapy. Randomization will include an allocation ratio of 2:1 (control:treatment).

Two 'site to participant' contacts are required during this study. These contacts can either occur at the clinical site or remotely (e.g., by telephone). During the initial contact, their interest in the study and eligibility will be confirmed, then they will be consented, asked to complete the Baseline Questionnaire, and their demographic information will be collected on case report forms (CRFs).

Participants randomized to the intervention (Group B) will be provided with information and assistance in downloading Restful to their smartphone and registering with Wellth.

At the final contact (90 days), the participant will be asked to complete an End of Study Questionnaire and the investigative staff will collect PAP therapy data for the trial period and record it on CRFs. Participants in Group B will have access to the Restful app discontinued. This completes the participant's active participation in the study.

Daily usage data from AirView will be collected and transmitted electronically from usage initiation to 90 days, and then through 180 days.

Study data will be captured on CRFs. See **Appendix A** for the **Baseline and End of Study Questionnaires**. See **Appendix B** for **Participant Instructions** related to the study procedures and the Restful app.

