3.3 NUMBER OF PARTICIPANTS

Up to 200 participants will be enrolled in the control arm and up to 100 participants will be enrolled in the treatment arm for a total of up to 300 participants enrolled in the study.

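### The exploratory engagement regression pools both arms with controls fixed at zero and no arm term, so its slope mixes the randomized arm difference with the engagement association in unknown proportion

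*Combined protocol and SAP*

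**What the plan says.** Section 3.9 sets the aim: "An exploratory analysis will examine how engagement with the study is associated with PAP usage". The measure is a count: "Engagement will be measured as app usage (number of touches"). The model is: "A linear regression model with PAP usage as the dependent variable and engagement as the independent variable will be fit to all ITT subjects". The same sentence gives the coding for controls in a parenthesis, "fit to all ITT subjects (engagement is zero for all control subjects"), so the zeros are deliberate.

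Engagement is the only regressor named. Other models in Section 3.9 do name randomized group: the primary ANOVA, the adherence logistic model, the ESS/FOSQ mixed model and the moderator model. No engagement fit restricted to Group B is planned. The documents give no mean, SD or distribution for touches.

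**The concern.** A control's zero and a Group B patient's zero mean different things. The first had no app to touch; the second had it and did not use it. Putting both at the same point on the engagement axis lets the difference between arms tilt the fitted line. That difference is already the subject of the primary analysis. What this analysis asks is whether patients who engage more use PAP more, and only Group B can answer it.

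If the intervention raises usage, the pooled slope tends to be positive even when touches and usage are unrelated among app users. A reader of the results could then take the arm effect for an engagement relation.

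**Working it through.** **Inputs from the documents**
- Allocation (Section 3.2): "Randomization will include an allocation ratio of 2:1 (control:treatment"), so the control share is q = 2/3.
- Enrolment (Section 3.3): 200 control, 100 intervention.
- Section 3.6: "detecting a difference of 0.8 hours in mean usage"; SD 2.5 in control and 2.0 in test; one-sided 0.025; 80% power; "180 in Control group, 90 in Test group".

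**Assumed, because the documents are silent:** the CV of touches in Group B, taken from 0.3 to 2.0, and gamma-distributed touches.

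**Step 1. The plan's own figure.** With 180/90, SE = √(2.5²/180 + 2.0²/90) = √0.0792 = 0.281. Then 0.8/0.281 = 2.84, and 2.84 − 1.96 = 0.88, which gives about 81% power (80.8% with the noncentral t). Also 270/0.9 = 300. The sample size reproduces, so its inputs can be used here. The engagement regression has no stated figure of its own.

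**Step 2. What the pooled slope estimates.** Let p = 1/3 be the Group B share, m and s the mean and SD of touches in Group B, Δ the arm difference in usage, and β the slope within Group B. With touches equal to 0 in all controls:
- Var(touches) = p(s² + q·m²)
- Cov(touches, usage) = p(β·s² + q·m·Δ)

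Dividing, and writing CV = s/m:

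pooled slope = w·(Δ/m) + (1 − w)·β, with w = q/(q + CV²).

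The first term is the arm effect per mean number of touches. The second is the association that the analysis is meant to describe.

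**Step 3. Size.** Set β = 0 (no link within Group B) and Δ = 0.8 h. The expected slope is then 0.8·w hours per mean number of touches, all of it from the arm difference. The last column is from simulation with 200/100 patients, SD 2.5/2.0 and a two-sided 5% test; simulation error is about two percentage points.

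| CV of touches | w | 0.8·w (h) | Pooled slope significantly positive |
|---|---|---|---|
| 0.3 | 88% | 0.70 | 76% |
| 0.5 | 73% | 0.58 | 68% |
| 0.8 | 51% | 0.41 | 52% |
| 1.0 | 40% | 0.32 | 40% |
| 1.5 | 23% | 0.18 | 23% |
| 2.0 | 14% | 0.11 | 15% |

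The Group B-only fit is significant, in either direction, in about 5% of trials throughout.

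**Step 4. Where the arm difference carries most of the weight.** w exceeds one half when CV² < 2/3, that is, when CV is below about 0.82.

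**Step 5. Effect of an arm term.** With a free intercept for each arm, controls have no variation in touches and drop out of the slope, so the estimate equals the Group B-only slope. Its ordinary standard error still uses a residual variance pooled over arms: √[(199 × 6.25 + 98 × 4)/297] = 2.35, against 2.0 in Group B. At the plan's SDs that standard error is about 2.35/2.0 = 1.17 times as large.

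**The case against.** The analysis is exploratory, the text speaks only of association, and the zero coding is stated openly. No primary or secondary endpoint, and no sample-size decision, depends on it. All of this stands, and it limits the severity. It does not rescue the model: an exploratory label excuses low power or multiplicity, but not a coefficient that fails to answer the stated question.

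Three stronger readings are tempting, and the documents do not support them.

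- **The slope is mostly the arm effect.** This needs a CV of touches below about 0.82, which the documents do not establish. Group B patients who never onboard stay in the ITT population and, with skewed counts, could push the CV above that. The within-arm association would then carry more weight.
- **The pooled model also goes wrong when there is no arm effect but heavy PAP users open the app more.** In that case engagement really is associated with usage, which is what Section 3.9 asks. With a within-arm correlation of 0.5, the Group B-only fit is significant in about 99–100% of trials. The pooled fit is significant less often at modest spread, roughly 30% at CV 0.3 and 60% at CV 0.5. The pooled model dilutes that association; it does not invent it.
- **The plan makes a false dose-response claim.** It makes no dose-response or causal claim. The risk lies in how a significant slope might later be read.

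**Conclusion.** Wrong as written, at low severity: worth correcting, not essential. The slope confounds the randomized arm difference with the within-Group-B association, and the mixing proportion depends on a spread of touches that the documents do not give.

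The defect is present across the whole range examined: even at CV 2.0, a significantly positive pooled slope appears in about 15% of trials with no within-arm link. The percentages rest on the full 0.8 h design effect, the plan's SDs, complete 200/100 enrolment and gamma-distributed touches. A smaller true arm effect would lower them. The algebra in Step 2 rests on none of these except the 2:1 allocation.

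**What to change.** Change the sentence in Section 3.9 so that the engagement regression is fitted in Group B only, or so that randomized group is added to the model. Both give the same slope. The Group B-only fit is simpler and avoids the pooled residual variance; if the arm term is preferred, use standard errors that allow unequal variances. Report the mean and spread of touches, and the number of Group B patients with none.

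Continue to report the slope as an association. The change removes the arm difference but not reverse influence: under Section 5.1, social currency is sent after a run of successful nights, so usage can itself generate app activity.

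Cost: one sentence and no new data, because Section 4.4 already provides user-level Restful engagement reports. The slope will rest on about 100 patients instead of 300, but the controls carry no information on the within-arm association, so little real precision is lost.

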The social incentive will have two components: social currency and social support messages. Participants will have the opportunity to nominate a social support person during the Wellth onboarding process. This person will be contacted directly by Wellth via text message and provided with information that will explain their role in supporting the participant. The support person will be asked to provide social currency (described below) that they think will be meaningful to the participant, as well as some supportive messages. Over the course of the 90-day trial, Wellth will reach out to the support person to solicit additional currency and messages. If the support person is generally non-responsive, or if the participant does not nominate a social support person, then the participant will receive Wellth-designed content for the social currency and social support components.

- Social currency: Pictures and/or videos that are meaningful to the participant. Delivered to the participant when they hit a therapy usage streak of 3 days in a row ≥ 4 hours.
- Social support messages: Encouraging messages that are meaningful to the participant. Delivered to the participant at seemingly random intervals throughout the 90 days (i.e., via a rules-based delivery algorithm).

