5.4 CONTROL GROUP

The control group will be monitored and managed per the site's standard of care with the exception of completion of questionnaires at baseline and again at 90 days after enrollment.

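### Support-person nomination exists only in Group B and only after randomization, so section 3.9 can report a within-arm association but cannot test moderation of the treatment effect

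*Combined protocol and SAP*

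**What the plan says.** The last exploratory analysis in section 3.9 of the protocol is to examine "whether nomination of, and the extent of engagement with, a social support person moderates the intervention effectiveness". No model, analysis population or comparator is given for it. For the baseline moderators, the same section does give a form: "the model will include baseline score, randomized group, and a randomized group by baseline score interaction as fixed effects".

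Section 5.1 states when nomination happens: "Participants will have the opportunity to nominate a social support person during the Wellth onboarding process". Three places tie that process to Group B:

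- Protocol Summary: "Those randomized to the intervention group will have a second contact, which involves onboarding to Restful".
- Section 3.2: "Participants randomized to the intervention (Group B) will be provided with information and assistance in downloading Restful to their smartphone and registering with Wellth".
- Section 4.2, under the step that follows randomization in the EDC: "Participants randomized to the Treatment group (Group B) will complete a set of baseline questionnaires and provided with instructions to download Restful to their smartphone".

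For controls, section 5.4 says: "The control group will be monitored and managed per the site's standard of care with the exception of completion of questionnaires". Nothing in the documents gives a control the chance to nominate anyone.

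Section 5.1 also has a fallback. A participant who nominates nobody, or whose support person is generally unresponsive, gets social content designed by Wellth.

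**The concern.** Moderation means that the Control-versus-Test difference changes with the level of some characteristic. To estimate it, that characteristic must be known in both arms, and it should not itself be a product of allocation. Nomination and engagement with a support person fail on both counts: they are features of the intervention and arise after randomization.

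At stake is how the result is read. Section 1 describes the social support element as novel and of particular interest, and the two arms otherwise differ by the whole financial-plus-social package. A difference between participants who chose to nominate and those who did not, reported as moderation, could be taken to mean that a support person makes the intervention work better. It could equally reflect who chooses to nominate. Section 1 itself lists social support among the factors that help to explain non-adherence.

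**Working it through.** **The plan's own figure.** The documents give no number for this analysis. The sample size in section 3.6 supplies the SD and group sizes used below, so it was reproduced first. Inputs: difference 0.8 h, SD 2.5 (Control) and 2.0 (Test), 180 and 90 patients, one-sided 0.025.

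- SE = sqrt(2.5²/180 + 2.0²/90) = sqrt(0.0347 + 0.0444) = 0.281 h.
- Noncentrality = 0.8/0.281 = 2.84. With Satterthwaite df 216.6, power is 80.8%.
- The smallest 2:1 total reaching 80% is 267 (178/89), against 270 stated; 270/0.9 = 300.

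The figure reproduces, and it has no bearing on whether moderation can be estimated.

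**Can the interaction be estimated?** Let G = 1 for Group B and M = 1 for a nominator. The usual moderator model is

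E(Y) = b0 + b1·G + b2·M + b3·G·M.

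With M = 0 for every control, the cell means are:

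| Cell | Mean |
|---|---|
| Control, M = 0 | b0 |
| Control, M = 1 | no patients |
| Group B, M = 0 | b0 + b1 |
| Group B, M = 1 | b0 + b1 + b2 + b3 |

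Three observed means cannot determine four coefficients. M and G·M are identical for every patient, so only the sum b2 + b3 can be estimated. That sum is the nominator-minus-non-nominator difference inside Group B.

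A numerical check used 200 controls and 100 Group B patients, with 30%, 50% or 70% nominating. These shares are assumptions, because the documents give none.

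- Nomination: rank 3 of 4 at every share.
- Engagement count, zero in controls: rank 3 of 4.
- Both together: rank 4 of 6.

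A larger trial would not change this. Setting controls to zero, as section 3.9 does for app touches, also calls every control a non-nominator, including those who would have nominated if asked. Comparing each Group B subset with all controls sets a self-selected group against an unselected one.

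**What the remaining contrast can show.** Take SD 2.0 (section 3.6), two-sided 0.05, 80% power and the normal approximation, with n1 nominators and n2 non-nominators:

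- SE = 2.0 × sqrt(1/n1 + 1/n2)
- Minimum detectable difference = (1.960 + 0.842) × SE
- Power for 0.8 h = Φ(0.8/SE − 1.960)

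| Group B | Nominating | n1/n2 | SE (h) | Detectable difference (h) | Power for 0.8 h |
|---|---|---|---|---|---|
| 90 | 50% | 45/45 | 0.422 | 1.18 | 48% |
| 90 | 30% or 70% | 27/63 | 0.460 | 1.29 | 41% |
| 100 | 50% | 50/50 | 0.400 | 1.12 | 52% |
| 100 | 30% or 70% | 30/70 | 0.436 | 1.22 | 45% |

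These figures describe precision only. They say nothing about the size of any selection bias.

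**The case against.** The strongest reply is that section 3.9 never commits to a group-by-nomination interaction. That form is written only for disease severity, claustrophobia, coping skills and health literacy. The sentence on support persons could mean a comparison among app users, which is feasible, in an analysis already labelled exploratory. It stands that a Group B analysis can be run and that the trial's main results do not depend on it. The reply does not rescue the stated aim, however: a within-arm association between a participant's choice and usage is not moderation of the intervention's effect, whichever model is fitted to it.

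A reader might infer that the analysis would pass off a selection effect as proof that the social component works. The documents do not support that. Under the section 5.1 fallback, non-nominators are given social content too, so the contrast concerns a nominated supporter against Wellth-designed content, not the social component against none. It is blurred further because nominators with an unresponsive supporter get the same fallback. Section 3.9 also does not say what conclusion would be drawn.

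A reader might also infer that the contrast is wholly selection. No figure in the documents supports any size for the bias. Section 3.9 names social support among its psychosocial factors, and a baseline measure of it, if collected, would allow some adjustment. The Appendix A items are not available here, so a suitable baseline item asked of both arms cannot be excluded. Even so, the planned analysis names nomination and engagement themselves, not such an item.

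**Conclusion.** The point holds in limited form. With the data the plan describes, moderation of the Control-versus-Test difference by nomination or engagement cannot be estimated, because both exist only in Group B. This is structural and does not depend on the nomination share. What can be estimated is a non-randomized comparison among about 90 to 100 Group B patients, open to confounding by motivation and existing social support. Its minimum detectable difference is roughly 1.12 to 1.29 h, and its power for the 0.8 h design difference is 41-52%, assuming SD 2.0 and 30-70% nominating. It is not evidence on the social component against none. The matter is minor: one exploratory analysis is misdescribed, and the primary and secondary results are untouched.

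**What to change.** Restate the analysis in section 3.9 as a descriptive association within Group B between usage and nomination, and between usage and extent of engagement. Adjust it for baseline social support if that is measured, report estimates with confidence intervals, and draw no moderation conclusion. Say how Group B participants who never complete onboarding are classified. This costs only wording.

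If a moderation test is wanted, collect one yes/no item from all participants asking whether they would name a support person, and test group by that answer as exploratory. The item belongs with the baseline data in step 2 of section 4.2. Adding it to the baseline questionnaires would not do, because section 4.2 lists those under step 3, after randomization in the EDC; in an open-label trial, participants could then answer knowing their arm. The cost is one extra item placed ahead of randomization. The limitation is that it records willingness to nominate, not actual nomination, and says nothing about extent of engagement.
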